4.4.14. Clinical Complement Tests (Both Cohorts)

For both cohorts, C3, C4, FD, and CH50 will be summarized at each visit by treatment group using descriptive statistics for the observed value as well as the change from baseline.

4.5. Safety Analyses

The safety and tolerability of ALXN2050 will be assessed based on adverse events (AEs), clinical laboratory findings, vital sign findings, electrocardiogram (ECG) abnormalities, and physical examination. All safety analyses will be performed on the SS based on the actual treatment received.

AEs will be coded in Medical Dictionary for Regulatory Activities (MedDRA) version 26.1 or higher and presented by MedDRA system organ class (SOC) and preferred term (PT).

All safety data will be provided in participant listings by treatment group. No formal hypothesis testing is planned. Safety data will be presented separately for the 26-week Blinded Initial Evaluation Period, 24-week Blinded Extended Treatment Period, and 2-year OLE Period.

4.5.1. Extent of Exposure

The cumulative and total drug exposure, compliance, and treatment duration will be summarized descriptively by treatment group for each disease cohort separately. The SS will be used for the analysis.

Treatment duration will be calculated (in weeks) as the difference between the date of last dose and the date of first dose plus 1, then divided by 7. The duration will be summarized with descriptive statistics.

Treatment compliance will be calculated as a percentage based on number of tablets received out of the number of tablets expected, where the number of tablets received= the number of tablets dispensed - the number of tablets returned; Number of tablets expected= 6 tablets/day × duration in number of days.

In addition to descriptive summary, the number and proportion of participants who had treatment compliance percentage in range by increments of 10% (eg, $\geq 90\%$ to $\leq 100\%$; $\geq 80\%$ to $\leq 90\%$; $\geq 70\%$ to $\leq 80\%$) will also be summarized by treatment group for each disease cohort separately.

The expected and received total dose amounts will be calculated as follows:

Expected total dose amount = assigned dose \times daily frequency (bid) \times duration in number of days

Received total dose amount = $60 \text{ mg} \times \text{number of tablets received}$

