6.1. Study Intervention(s) Administered

The interventions in this study are ALXN2050 and matching placebo. Study interventions are presented in Table 10. Allowed concomitant therapies are discussed in Section 6.5.3.1 and Section 6.5.3.2 for the LN and IgAN cohorts, respectively.

Table 10: Study Interventions

Study Intervention Name	ALXN2050	Placebo	
Dose formulation	Tablet	Tablet	
Physical description	Round, white to off-white film coated tablet	Round, white to off-white film coated tablet	
Unit dose strength(s)	60 mg	Placebo	
Dosage levels	120 mg bid or 180 mg twice daily	Not applicable	
Route of administration	Oral	Oral	
IMP or AxMP	IMP	IMP	
Use	Experimental	Placebo comparator	
Former Name	ACH-0145228	Not applicable	
Sourcing	Alexion Pharmaceuticals, Inc.	Alexion Pharmaceuticals, Inc.	

Abbreviations: AxMP = auxiliary medicinal product; bid = twice daily; IMP = investigational medicinal product

Participants will take study intervention bid (a dose of 3 tablets in the morning and a second [evening] dose of 3 tablets approximately 12 hours after the morning dose). Doses should be taken at approximately the same time each day. If a dose is missed, it should be taken within 6 hours of the originally scheduled time. After 6 hours, the missed dose should be skipped. In either case, the next dose should be taken according to the original dosing schedule. Information on missed doses should be recorded in the electronic case report form (eCRF).

Most doses will be taken outside of the clinic. Participants will be provided with sufficient study intervention to last until their next study visit.

For study visits that require PK sample collection, participants will be instructed to abstain from taking their ALXN2050 dose on the mornings of their study visits so that they can be dosed in the clinic following the protocol-required assessments. At the clinic visit, participants will first have blood drawn for clinical laboratory and other evaluations as outlined in the SoA (Section 1.3), then take the morning dose of ALXN2050 assigned for that day.

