Figure 2:	Study Design Schematic (IgAN Cohort)	18

VERSION HISTORY

This statistical analysis plan (SAP) for Study ALXN2050-NEPH-201 is based on Protocol Amendment 3.0, dated 21 Feb 2024.

SAP Version	Version Date	Change	Rationale
1.0	23 Nov 2022	Not applicable	Original version.
2.0	10 May 2023	Included the option to perform an early interim analysis	For Phase 3 planning purposes.
		Other minor edits	For clarity.
3.0	12 Nov 2024	Deleted data presentation for Safety Follow-up Period	Safety Follow-up Period is not a treatment period.
		Revised the derivation of the primary endpoint	Visit window is changed.
		Added ALXN2050 Total group into data presentation	To evaluate the overall ALXN2050 treatment effect.
		Changed terminologies: "background therapy" to "allowed concomitant therapy" and "rescue therapy" to "additional standard-of-care therapy"	To align with EU CTR requirements.
		Added an analysis of abnormal liver enzyme elevations	To evaluate drug-induced liver injury.
		Added a sensitivity analysis due to dosing pause	Screening, enrollment, and study intervention administration have been temporarily paused as of 06 September 2024.
		Other minor edits	For minor corrections.

APPROVAL SIGNATURES

Biostatistics	Date dd Mmm yyyy
Biostatistics	Date dd Mmm yyyy
	Date dd Mmm yyyy

LIST OF ABBREVIATIONS

Abbreviation	Definition
AE	adverse event
ALP	alkaline phosphatase
ALT	alanine aminotransferase
AP	alternative pathway
AST	aspartate aminotransferase
ATC	anatomical therapeutic chemical
Bb	Bb fragment of complement factor B
bid	twice daily
BLQ	below the limit of quantification
Clq	complement component C1q
C3	complement component 3
C4	complement component 4
CDF	cumulative distribution function
CI	confidence interval
CNI	calcineurin inhibitor
COVID-19	coronavirus disease 2019
CRR	complete renal response
cTTO	composite time trade-off
CV	coefficient of variation
CV%	coefficient of variation percentage
dsDNA	double-stranded DNA
EC	exclusion criteria
ECG	electrocardiogram
eCRF	electronic case report form
eGFR	estimated glomerular filtration rate
EQ-5D-5L	5-level EuroQol-5 Dimensions
FACIT-Fatigue	Functional Assessment of Chronic Illness Therapy – Fatigue Scale
FAS	Full Analysis Set
FD	factor D
GM	geometric mean
GMR	geometric mean ratio
hpf	high power field
IC	inclusion criteria
IE	intercurrent event

Abbreviation	Definition	
IgAN	immunoglobulin A nephropathy	
LLN	lower limit of normal	
LN	lupus nephritis	
MAR	missing-at-random	
MCS	Mental Component Summary	

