4.5.2. Adverse Events

The following definitions will be used for AEs:

- **Pretreatment AE:** Any AE that starts after providing informed consent, but before the first dose of study intervention (ALXN2050 or placebo)
- Treatment-emergent adverse event (TEAE): Any AE that starts between the start of the first dose of study intervention and up to 30 days after the last dose of study intervention
- Treatment-emergent serious adverse event (TESAE): A TEAE that is serious
- **Post-treatment AEs:** Any AE that starts 30 days or later after the last dose of study intervention

All AEs will be coded using MedDRA version 26.1 or higher and will be summarized by SOC and PT overall, by severity, and by relationship to treatment.

Participants having multiple AEs within a category (eg, overall, SOC, PT) will be counted once in that category. For severity/relationship tables, the participant's highest grade/most related event within a category will be counted.

TEAEs and serious adverse events (SAEs) will be summarized descriptively by treatment group. Percentages will be based on the number of treated participants in the SS within a treatment group. Tables will be sorted by descending frequency of SOC and by descending frequency of PT within an SOC.

Pretreatment and post-treatment AEs will be provided in by-participant listings and will not be included in summary tables.

In addition, AEs that occur after the receipt of additional standard of care therapy will be provided in a separate listing.

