6.1.7. Adverse Events

The analysis of AEs is described in detail in Section 4.5.2.

Treatment-emergent AEs (TEAEs) are events with start dates and start times on or after the date and time of the first dose of study intervention and up to 30 days after the last dose of study intervention. If the start date of an AE is partially or completely missing and the end (stop) date and time of the AE does not indicate that it occurred prior to first dose or 30 days after the last dose, then the determination of treatment-emergent status will be based on the following:

- If the start year is after the year of the first dose of study intervention and before the year of the last dose of study intervention, then the AE is treatment-emergent; else
- If the start year is the same as the year of the first dose of study intervention and
 - the start month is missing, then the AE is treatment-emergent; else, if
 - the start month is present and is the same or after the month of the first dose of study intervention and is the same or before the last dose of study intervention, then the AE is treatment-emergent; else,
- If the start date is completely missing, then the AE is treatment-emergent.

All other AEs are considered pretreatment adverse events (PTAEs) if the start date is prior to the first dose of study intervention or post-treatment adverse events if the start date is 30 days or later after the last dose of study intervention.

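### SAP 4.5.1 leaves the dosing pause inside treatment duration, so a participant who resumes dosing gets overstated duration and expected dose and understated compliance

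*SAP*

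**What the plan says.** **Exposure (SAP 4.5.1).** Duration uses only the two end dates: "Treatment duration will be calculated (in weeks) as the difference between the date of last dose and the date of first dose plus 1", divided by 7. For compliance, the denominator is "Number of tablets expected= 6 tablets/day × duration in number of days" and the numerator is "the number of tablets dispensed - the number of tablets returned". Expected total dose is assigned dose times daily frequency times the same duration in days. Compliance is also tabulated in 10% bands. No interruption term appears.

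**Tablets per day (Protocol 6.1).** The regimen is "a dose of 3 tablets in the morning and a second [evening] dose of 3 tablets", which agrees with the SAP's multiplier of 6.

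**The pause.** The SAP Version History, in the row for version 3.0, says that screening, enrollment and dosing "have been temporarily paused as of 06 September 2024". The SAP Introduction gives the same start date without calling the pause temporary. No restart date appears.

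**Where the pause is handled.** It enters the missing-data rule (SAP 4.1.4), the efficacy sensitivity analyses (4.2.3 and 4.3.2) and a count in the disposition summary (6.2.1). SAP 4.5, the safety section, does not mention it.

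**Treatment-emergent window.** Under SAP 4.5.2, an event is treatment-emergent if it "starts between the start of the first dose of study intervention and up to 30 days after the last dose" of study intervention. SAP 6.1.7 gives the same end point: "and up to 30 days after the last dose of study intervention".

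**Recorded dates.** Protocol 6.4 requires intervention start and stop dates to be recorded, including the dates of planned and unplanned delays.

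**The concern.** Version 3.0 was written with the pause in view, yet the exposure derivations were left unchanged. One efficacy sensitivity analysis treats the pause like treatment discontinuation, while SAP 4.5.1 counts the same days as time on treatment for anyone who later resumes. The SAP gives no reason for the difference.

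The compliance ratio is where this does most damage. Its numerator counts tablets and so reflects only time when tablets were supplied. Its denominator counts calendar days and so includes the pause. The two cover different time, and the shortfall looks like non-adherence by the participant. A reader of the exposure tables would see more weeks of treatment than were given and lower compliance than occurred.

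**Working it through.** **Inputs**
- Duration, expected-tablet and received-tablet rules: SAP 4.5.1.
- Tablets per day: 3 + 3 = 6 (Protocol 6.1).
- T, days from first to last dose: 350 (50 weeks) or 182 (26 weeks), for illustration.
- P, pause days: not in the documents, so assumed. The main range is 8 to 12 weeks (56 to 84 days). One anchor is 67 days, from 06 September 2024 to the version 3.0 date of 12 November 2024: 24 + 31 + 12 = 67.
- The participant takes every tablet due while dosing is open, resumes after the pause, and keeps no unreturned tablets from before it.

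The plan states no figure of its own to reproduce.

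**Formulas**
- SAP duration = T; days on drug = T − P.
- Expected tablets under the SAP = 6T; with the pause removed = 6(T − P).
- Tablets received = 6(T − P).
- SAP compliance = 6(T − P) / 6T = (T − P) / T.
- Overstatement of duration, and of expected dose, = T / (T − P) − 1.

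**Results**

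| T | P | Weeks on drug | Expected tablets, SAP | Expected tablets, pause removed | SAP compliance |
|---|---|---|---|---|---|
| 350 | 56 | 42 | 2100 | 1764 | 294/350 = 84% |
| 350 | 84 | 38 | 2100 | 1596 | 266/350 = 76% |
| 350 | 67 | 40.4 | 2100 | 1698 | 283/350 = 80.9% |
| 182 | 28 | 22 | 1092 | 924 | 154/182 = 84.6% |
| 182 | 67 | 16.4 | 1092 | 690 | 115/182 = 63.2% |

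For 8 and 12 weeks in 50, the overstatement of duration is 50/42 = 1.19 and 50/38 = 1.32, that is 19% and 32%. With the pause removed, compliance is 100% in every row. In the 10% bands of SAP 4.5.1, values of 84%, 76% and 63% put a fully adherent participant one, two and three bands too low.

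**If dosing does not resume.** The last dose then precedes the pause, so P lies outside the first-to-last-dose span and every quantity above is correct as written.

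**Adverse events.** The first 30 days off drug fall within the ordinary 30-day tail. Off-drug days beyond it that still count as treatment-emergent number max(0, P − 30): 26 for P = 56, 37 for P = 67, 54 for P = 84, and none for a pause of 30 days or less.

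**The case against.** **The effect is conditional.** The documents do not show that anyone resumed, and without resumption the formulas work. This stands, and it is why the point is limited to participants who resume. The Version History does call the pause temporary, so the plan should cover resumption.

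**The downstream reach is small.** Adverse event percentages use the number of treated participants, and the SAP specifies no exposure-adjusted rates, so inflated duration enters no adverse event statistic. Received total dose is built from tablet counts and a pause does not inflate it. Both points stand. What is affected is descriptive: duration, expected dose and compliance.

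**The 50-week span is not a reporting unit.** SAP 4.1 and 4.5 present safety separately for the 26-week, 24-week and open-label periods, so the distortion per period may be larger, smaller or nil. This stands. The 26-week rows show that the same pause weighs more in a shorter span.

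**The treatment-emergent window is a legitimate convention.** A reader might infer that off-drug events are wrongly classed as treatment-emergent and that the window should close and reopen around the pause. The documents do not support calling this an error. One continuous window is conservative because it keeps delayed events in the tables. SAP 4.5.2 keeps post-treatment events out of the summary tables, so moving pause events to listings alone would take late events out of view. Placebo follows the same rule, and no bias between arms is shown. What remains is that the planned tables do not distinguish onset on drug from onset long after the drug was stopped.

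**The liver table.** A reader might also infer that the liver-enzyme table added in version 3.0 inherits the problem. SAP 4.5.3.1 does not define its during-treatment category, so this cannot be established. The SAP does not give the reason for the pause, and it lists the liver table and the pause analyses as separate changes with separate rationales.

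**Detail may exist elsewhere.** Table and listing specifications are in a separate Data Presentation Plan that is not available here. A rule there could help, but the formulas in 4.5.1 are explicit and would need to agree with it.

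**Conclusion.** The point holds for exposure and compliance. For any participant who resumes dosing, SAP 4.5.1 as written overstates duration and expected dose and understates compliance. On an assumed pause of 8 to 12 weeks within 50 weeks, duration is overstated by 19% to 32%, and full adherence appears as 84% to 76%. A 67-day pause within 26 weeks gives 63%. These sizes rest on an assumed pause length and on resumption, and the documents establish neither. The effect is nil if dosing does not resume.

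The treatment-emergent definition is not wrong, and the effect on the liver table is unproven; both call only for an added display. A reader might also infer that adherent participants would drop out of the Per-Protocol Set, which requires more than 80% of planned dose in the first 26 weeks. Within 182 days, a pause longer than 0.20 × 182 = 36.4 days would take the 4.5.1 compliance figure below 80%. However, the SAP does not say that planned dose there means the expected amount in 4.5.1, so that consequence does not follow from the text. The primary hypothesis test does not use the 4.5.1 formulas.

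**What to change.** 1. **SAP 4.5.1.** Base duration on drug, expected tablets and expected total dose on days from first to last dose minus documented pause days, counting in each reporting period only the pause days that fall in it. Optionally show the first-to-last-dose span as a second, labelled measure.
2. **SAP 4.5.2 and 6.1.7.** Leave the treatment-emergent window unchanged. Add a flag or separate tabulation, by treatment group, of adverse events that start more than 30 days after the last pre-pause dose and before the first resumed dose. Keep these events in the main summary tables.
3. **SAP 4.5.3.1.** Apply the same flag to liver elevations, and state which dates the during-treatment category covers.

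The cost is a few sentences of SAP wording, one derived pause-days variable and one additional display. Protocol 6.4 already requires the necessary dates, so no new data collection is needed. Study conduct and hypothesis tests are unchanged.

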All participants will continue to receive allowed concomitant therapy consistent with the standard of care for participants with LN and IgAN throughout the study. Participants in the LN cohort will receive additional standard of care therapy in the event of a protocol-defined Renal Flare or severe Extrarenal systemic lupus erythematosus (SLE) Flare and after Week 26, for Suboptimal Response. Approved novel treatments for LN can be used per the Investigator's discretion. However, if additional standard of care therapy is initiated, the Investigator should consult the list of disallowed medications (Section 6.5.2). If additional standard of care therapy is a prohibited medication, study intervention should be discontinued at least 3 days prior to initiation of the additional standard of care therapy.

Blinded Initial Evaluation Period

- For each disease cohort, participants will be randomly assigned in a 3:1:3 ratio on Day 1 to receive ALXN2050 180 mg twice daily (bid), ALXN2050 120 mg bid, or placebo bid throughout the Blinded Initial Evaluation Period (26 weeks).
- For the IgAN cohort, participants assigned to the placebo group on Day 1 will also be assigned to their study treatment for the Blinded Extended Treatment Period (ALXN2050 180 mg bid or ALXN2050 120 mg bid) in a 1:1 allocation ratio at the time of randomization.

Blinded Extended Treatment Period

After completion of the Blinded Initial Evaluation Period (Week 26), participants will continue to receive study intervention during a Blinded Extended Treatment Period for 24 weeks as follows:

 Participants in the LN cohort will continue to receive their randomized allocation of study intervention (ALXN2050 180 mg, ALXN2050 120 mg, or placebo) bid. After Week 26, additional standard of care therapy for participants with Suboptimal Response is allowed at the clinical discretion of the Investigator in conversation with the Medical Monitor.

- Participants in the IgAN cohort randomized to the ALXN2050 180 mg bid or ALXN2050 120 mg bid groups will continue to receive their randomized allocation of study intervention bid.
- Participants in the IgAN cohort randomized to the placebo group will receive either ALXN2050 180 mg bid (n = 12) or ALXN2050 120 mg bid (n = 12) as assigned at the time of randomization.

Open-Label Extension Period

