6.1.1. Blinded Treatment

ALXN2050 and placebo tablets will be identical in appearance. The blinded study interventions are shown in Table 11.

Table 11: Blinded Study Intervention from Week 1 to Week 50 in Addition to Allowed Concomitant Therapy

	Dose Group		
Timing	ALXN2050 120 mg bid	ALXN2050 180 mg bid	Placebo
Morning dose	60 mg	60 mg	Placebo
	60 mg	60 mg	Placebo
	Placebo	60 mg	Placebo
Approximately 12 hours interval			
Evening dose	60 mg	60 mg	Placebo
	60 mg	60 mg	Placebo
	Placebo	60 mg	Placebo

Abbreviation: bid = twice daily

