9.4.8. PK/PD Analysis for Both LN Cohort and IgAN Cohort

Descriptive statistics will be calculated for plasma concentration data at each sampling time, as appropriate. Observed trough concentrations (C_{trough}) and serum C_{max} will be summarized.

The PD effects of ALXN2050 will be evaluated by assessing the absolute values and changes and percentage changes from baseline in serum AP activity and plasma Bb concentration over time, as appropriate. Descriptive statistics will be calculated for the PD data at each sampling time, as appropriate.

Population PK modeling will be conducted to characterize the PK of ALXN2050 in participants who are on the active treatment. Covariates (source of variability) that have significant impact on the PK will be identified. Steady state exposure parameters such as the area under the concentration-time curve (AUC) and the C_{max} will be derived from the Population PK model. In addition, a PK-PD model will be developed. Factors contributing to the PK-PD relationship will also be explored. Maximum PD response and the exposure required to achieve 50% of the response will be presented. Actual dose administration and sampling times will be used for Population PK and PK-PD analyses.

Details of Population PK modeling, as well as PK-PD modeling, will be presented in a Population PK/PD Analysis Plan. Results from Population PK/PD analyses will be presented in a separate Population PK/PD Analysis Report.

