4.1.2. Data Presentation for the 24-Week Blinded Extension Treatment Period

For the LN cohort, data summaries for the 24-week Blinded Extension Treatment Period will be presented by randomized treatment group and total when applicable.

For the IgAN cohort, summaries will be presented by treatment sequence (ie, "ALXN2050 180 mg", "ALXN2050 120 mg" and "Placebo to ALXN2050 180 mg" or "Placebo to ALXN2050 120 mg"). ALXN2050 Total, which consists of all the participants who were treated with ALXN2050 during the 24-week Blinded Extended Treatment Period, will be added when applicable. "ALXN2050 120 mg & 180 mg" which consists of participants who initially randomized to ALXN2050, will be included in efficacy tables when applicable. In addition, the baseline for the IgAN cohort will be defined as the originally randomized baseline and re-baseline will be defined as the last measurement collected prior to Week 26.

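### The SAP's received-dose formula credits 60 mg to every tablet, so the 120 mg arm's exposure is overstated by 50% in the blinded periods

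*SAP*

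**What the plan says.** SAP section 4.5.1 defines four quantities for the Safety Set exposure summary:

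- Tablets received: "the number of tablets received= the number of tablets dispensed - the number of tablets returned".
- Tablets expected: "Number of tablets expected= 6 tablets/day × duration in number of days", the same in every arm.
- Expected dose: assigned dose, times two for twice-daily dosing, times days of treatment.
- Received dose: "Received total dose amount = $60 \text{ mg} \times \text{number of tablets received".

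None of these carries an arm-specific tablet strength or is limited to active tablets.

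Protocol section 6.1 has every participant take "a dose of 3 tablets in the morning and a second [evening] dose of 3 tablets". Table 11 in Protocol section 6.1.1, titled "Blinded Study Intervention from Week 1 to Week 50 in Addition to Allowed Concomitant Therapy", gives the make-up of each dose: three 60 mg tablets in the 180 mg group, two 60 mg tablets and one placebo tablet in the 120 mg group, and three placebo tablets in the placebo group.

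**The concern.** The blind is kept by giving all arms the same number of tablets, so the tablet count says nothing about dose. Multiplying that count by 60 mg is right only for the 180 mg arm. In the 120 mg arm it counts the placebo tablet as drug.

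This is a dose-finding trial, and the exposure table is where a reader checks how much drug each arm took before comparing adverse events by dose. With the formula as written, the two active arms would show the same received milligrams at equal compliance, although their assigned doses differ by one third. The pooled ALXN2050 column would carry part of the same error. Read literally, the formula also gives placebo participants a nonzero ALXN2050 dose, since the SAP does not restrict it to the active arms.

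**Working it through.** **Inputs.** Six tablets a day (3 × 2, Protocol 6.1; the SAP's figure reproduces). Active tablets per day from Table 11: 6, 4 and 0 for 180 mg, 120 mg and placebo. Planned numbers on 180 mg and 120 mg from Protocol Table 8: LN 30 and 10, IgAN 24 and 8. IgAN placebo participants then switch to "ALXN2050 180 mg bid (n = 12) or ALXN2050 120 mg bid (n = 12") in the extended period.

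**Per day, full compliance.** Expected = assigned dose × 2. SAP received = 60 × all tablets. Actual = 60 × active tablets.

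| Arm | Expected | SAP received | Actual | SAP / actual |
|---|---|---|---|---|
| 180 mg | 180 × 2 = 360 | 60 × 6 = 360 | 60 × 6 = 360 | 1.00 |
| 120 mg | 120 × 2 = 240 | 60 × 6 = 360 | 60 × 4 = 240 | 1.50 |
| Placebo | 0 | 60 × 6 = 360 | 0 | – |

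**Cumulative, 120 mg arm.**

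- Initial period, 26 × 7 = 182 days: 360 × 182 = 65,520 mg against 240 × 182 = 43,680 mg.
- Extended period, 24 × 7 = 168 days: 360 × 168 = 60,480 mg against 240 × 168 = 40,320 mg.
- If the Day 351 dose is counted under the SAP's inclusive duration rule, the extended period is 351 − 183 + 1 = 169 days: 60,840 mg against 40,560 mg. The ratio is still 1.50.

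**Can another reading of tablets received rescue the formula?** Suppose it means active tablets only. Received dose in the 120 mg arm is then 60 × 4 = 240 mg/day, which matches the expected dose. But the same count is the compliance numerator over six tablets, so full compliance becomes 4/6 = 66.7%. If all tablets count, compliance is 100% and the dose ratio is 150%. No single reading makes both formulas work for this arm.

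**Pooled ALXN2050, initial period.** LN: (30 × 360 + 10 × 240)/40 = 330 mg/day. IgAN: (24 × 360 + 8 × 240)/32 = 330 mg/day. The SAP formula gives 360, and 360/330 = 1.091, or +9.1%.

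**IgAN pooled, extended period.** SAP section 4.1.2 defines "ALXN2050 Total, which consists of all the participants who were treated with ALXN2050 during the 24-week Blinded Extended Treatment Period". That is 24 + 12 = 36 on 180 mg and 8 + 12 = 20 on 120 mg. The actual mean is (36 × 360 + 20 × 240)/56 = 317.1 mg/day, and 360/317.1 = 1.135, or +13.5%.

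**Incomplete compliance, 120 mg arm, 90% of tablets taken (5.4 a day, 0.6 missed).** The SAP formula gives 60 × 5.4 = 324 mg/day. The actual dose depends on which tablets are missed:

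- All missed tablets active: (4 − 0.6) × 60 = 204 mg/day (85% of 240); overstatement 324/204 = 1.59.
- Missed in the 2:1 active-to-placebo proportion: 5.4 × 40 = 216 mg/day (90%); overstatement 324/216 = 1.50.
- All missed tablets placebo: 240 mg/day (100%); overstatement 324/240 = 1.35.

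**The case against.** The strongest counter-argument is about weight. The error sits in a descriptive table. About 10 + 8 = 18 of the 126 planned participants are in the 120 mg arm initially, with 12 more IgAN participants switching to that dose at Week 26. A received dose at 150% of expected beside 100% tablet compliance might well be noticed at programming. A programmer is also unlikely to print ALXN2050 milligrams for placebo participants. All of this is fair. It makes the point a correction rather than a threat to the trial's conclusions, but the SAP should not depend on someone noticing that its stated formula is wrong.

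The pooled figures are illustrative. They assume planned numbers and full compliance, whereas the plan anticipates 10% dropout and dosing was paused from 06 September 2024. For the extended period, the SAP adds the pooled group only where applicable, so the 13.5% might never appear in a table. The initial-period figure is better founded, because SAP section 4.1.1 lists the pooled group among the groups presented.

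An average of 40 mg per tablet is also only second best: if active and placebo tablets can be counted separately, 60 mg times active tablets taken is exact. The documents do not say how the 120 mg kits are packed, so the fix allows for both cases. None of these objections removes the contradiction between SAP 4.5.1 and Table 11.

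**Conclusion.** The formula is wrong as written for the 120 mg arm in both blinded periods, and it should be fixed. The overstatement is 50% at full compliance, or at any compliance if tablets are missed in the 2:1 active-to-placebo proportion. At 90% of tablets taken it could lie between 35% and 59%. The 180 mg arm is unaffected.

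The reach is limited. The primary efficacy analysis, tablet-count compliance, treatment duration and plasma concentration summaries do not use the formula. Nor does the population modelling: Protocol section 9.4.8 states that "Actual dose administration and sampling times will be used for Population PK and PK-PD analyses".

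Membership of the Per-Protocol Set (more than 80% of planned dose received) or of the mFAS (more than 20% of dose missed because of COVID-19) would be affected only if those rules used the uncorrected milligram ratio, which the SAP does not specify. If the Per-Protocol rule did, a 120 mg participant would reach the 80% threshold at 0.8/1.5 = 53.3% of tablets. No open-label error can be shown, because Table 11 stops at Week 50.

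**What to change.** In SAP section 4.5.1, replace the received-dose formula for the blinded periods with (assigned dose / 3) × tablets received. That is 60, 40 or 0 mg per tablet for 180 mg, 120 mg or placebo, applied by period so that IgAN participants who switch from placebo are handled correctly. State that this assumes tablets are missed in the 2:1 active-to-placebo proportion. Where kit records separate the two tablet types, use 60 mg × active tablets taken instead.

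Two secondary clarifications belong in the same edit:

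- For the open-label period, define received dose and tablets expected per day from the tablet make-up actually dispensed.
- In SAP section 3, state that the Per-Protocol rule uses the tablet-count percentage and that the mFAS rule does not use 60 mg times all tablets.

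The cost is one formula, two clarifying sentences and the derived-variable programming. The blinded-period correction needs no data beyond the tablet counts and assigned doses already collected.
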